- 1.2.8. To evaluate the impact of delayed start olaparib in platinum sensitive recurrent epithelial ovarian caner with a complete or partial response to last platinum therapy on worry and distress
 - 1.2.8.1. Endpoint: Worry and distress measured via Assessment of Survivor Concerns (ASC) Worry Subscale and Impact of Event Scale (IES-R).
- 1.2.9. To evaluate the impact of delayed start olaparib in platinum sensitive recurrent epithelial ovarian cancer with a complete or partial response to last platinum therapy on financial toxicity
 - 1.2.9.1. Endpoint: Financial toxicity measured through (a) monetary measure using the Modified Collection of Indirect and Nonmedical Direct Costs (COIN), (b) objective measure of financial burden assessed using Barrera et al's Economic Hardship questionnaire⁵¹, and (c) subjective measure of financial distress will be gauged using the Comprehensive Score for Financial Toxicity (COST Measure).
- 1.2.10. To explore exposure-response relationships between olaparib exposure and toxicity/efficacy.
 - 1.2.10.1. Endpoint: Exposure as expressed by day 28 trough olaparib concentration measured by LC-MS/MS.

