8.1. Adverse Events and Potential Risks List for Olaparib

>10%:

Cardiovascular: peripheral edema (14%)

Central nervous system: fatigue (≤67%), headache (15% to 26%), dizziness (7% to 20%)

Endocrine & metabolic: hypomagnesemia (5% to 14%)

Gastrointestinal: nausea (58% to 77%), abdominal pain (45%), vomiting (30% to 43%), diarrhea (21% to 37%), constipation (16% to 28%), dysgeusia (9% to 27%), dyspepsia (8% to 25%), decreased appetite (16% to 22%), stomatitis (4% to 20%; grades 3/4: 1%)

Genitourinary: urinary tract infection (13% to 14%)

Hematologic & oncologic: increased MCV (57% to 89%), decrease in absolute neutrophil count (25% to 51%; grades 3/4: 7% to 11%), anemia (23% to 44%; grades 3/4: 7% to 21%), neutropenia (5% to 27%; grades 3/4: 6% to 9%), leukopenia (2% to 25%; grades 3/4: 3% to 5%), thrombocytopenia (4% to 14%; grades 3/4: 1%)

Infection: influenza ($\leq 36\%$)

Neuromuscular & skeletal: asthenia ($\leq 66\%$), arthralgia ($\leq 30\%$), myalgia ($\leq 30\%$), musculoskeletal pain ($\leq 21\%$), back pain (14%)

Renal: increased serum creatinine (3% to 45%)

Respiratory: nasopharyngitis (\leq 36%), respiratory tract infection (\leq 36%), rhinitis (\leq 36%), sinusitis (\leq 36%), bronchitis (\leq 28%), cough (16% to 18%), dyspnea (13% to 15%)

1% to 10%:

Cardiovascular: edema (8% to 9%), pulmonary embolism (\leq 1%), venous thrombosis (\leq 1%)

Central nervous system: peripheral neuropathy (5%), depression, insomnia

Dermatologic: skin rash (5% to 6%), dermatitis (1%)

Gastrointestinal: upper abdominal pain (7%)

Hematologic & oncologic: lymphocytopenia (1% to 8%), myelodysplastic syndrome (acute myeloid leukemia; 1%)

Hypersensitivity: hypersensitivity reaction (2%)

Miscellaneous: fever (8% to 10%)

<1%, postmarketing, and/or case reports: pneumonitis

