exposure and toxicity/efficacy. A steady-state trough sample will be obtained around day 28. Trough concentrations (if need be corrected for time since dosing) will be compared between patients with/without response and patients with/without toxicity. This assay will be performed at the UPMC Hillman Cancer Center Cancer Pharmacokineitc and Pharmacodynamics Facility. (CPPF). The published olaparib assay has successfully been implemented and is available (Nijenhuis et al. Journal of Chromatography B, 940 (2013) 121–125). Note: plan the patient's day 28 visit such that their blood can be drawn at about the time they would otherwise take their dose, but **BEFORE** they take it. Ask patients to take bring their olaparib so they can take their dose after their PK blood draw. See appendix D for practical details.

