- H. Financial toxicity will be measured through a) monetary measure using the Modified Collection of Indirect and Nonmedical Direct Costs (COIN) (See Appendix I), b) objective measure of financial burden assessed using Barrera et al.'s Economic Hardship questionnaire (See Appendix J), and c) subjective measure of financial distress will be gauged using the Comprehensive Score for Financial Toxicity (COST Measure) (See Appendix K).
- I. Pregnancy test for women of childbearing potential (WOCBP) must be done within 24 hours prior to initiation of olaparib.
- J. Tissue collection is not mandatory. If permission granted, tissue prior to initiation on olaparib will be obtained from archival stores. If patient undergoes biopsy at the time of progression as part of standard of care, tissue will be collected after routine processing.
- K. A mandatory trough plasma sample will be obtained only once at approximately 28 days after initiation of treatment (See **Appendix L**).
- L. BRCA testing required (Results not needed for registration
- M. Chart review or office visit every 3 months for 18 months from time of enrollment

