13.2 SAMPLE SIZE/ACCRUAL RATE

Study 19 is the only PARP inhibitor maintenance trial in the platinum sensitive recurrent setting to report both PFS and OS data. Median progression-free survival was 8.4 months in the olaparib group versus 4.8 months in the placebo group (hazard ratio for progression or death, 0.35; 95% confidence interval [CI], 0.25 to 0.49; P<0.001). The secondary end point of time to progression according to the RECIST guidelines or CA-125 level, whichever showed earlier progression, was also significantly longer in the olaparib group than in the placebo group (median, 8.3 months vs. 3.7 months; hazard ratio for progression, 0.35; 95% CI, 0.25 to 0.47; P<0.001). There was no statistically significant OS advantage noted for those treated with olaparib; for the entire population median OS was 29.8-months-[95%-CI-26·9–35·7]-in the olaparib arm vs 27.8 months-[24·9–33·7] in the placebo arm. For those patients evaluable for response (n=61), there were 16 (26.2%) either PR or CR by RECIST and 1 (1.6%) by CA125²⁹.

Using the reported data from Study 19, we will assess whether delaying olaparib until biochemical relapse will increase the median time to next treatment by \sim 3 months (from 8 to 11 months). We assume 3-4 patients can be accrued/month and that the *BRCA* mutation

prevalence will be ~20% and thereby be comparable to the historical control group. With 2 years of accrual and 18 months of additional follow up, we will require 75 eligible patients. This will allow 90% power for a level 0.10 one-sided one sample exponential test to detect an improvement in median time to next treatment from 8 to 11 months. Due to the possibility of lost to long-term follow-up, we plan to accrue an additional 10% of the targeted accrual. Therefore, the sample size for this study will be approximately 83 patients in order to successfully accrue 75 evaluable patients.

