13.3.3 Analysis of Safety Endpoints

The NCI common terminology criteria for adverse events (CTCAE 5.0) will be used to evaluate toxicity; we will consider a toxicity to be an adverse event that is possibly, probably or definitely related to treatment. The maximum grade of toxicity for each category of interest will be recorded for each patient and the summary results will be tabulated by category and grade. Statistics on the number of cycles received by patients and any dose reductions will also be tabulated.

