13.3.5 Analysis of Patient Reported Outcomes, Quality of Life and Financial Toxicity Endpoints

Additional **Secondary Endpoints** include a series of quality of life instruments and financial toxicity measures. These instruments will be administered starting at onset of trial enrollment and periodically thereafter. Patient reported adverse events, worry and distress (3 instruments measured every 4 weeks), health related quality of life, physical functioning and financial toxicity (5 instruments measured every 12 weeks) will provide data for longitudinal analysis with mixed effects linear models. We will focus on change over time particularly between the two treatment periods, pre and post olaparib. Our linear mixed effects models will emphasize random coefficients that allow non-linear profiles, typically polynomial regression, restricted cubic splines or piecewise linear splines with a knot to represent the time of starting olaparib. These models will permit us to estimate whether quality of life and financial toxicity change over the course of the clinical trial and, in particular, whether the observed change suggests a shift that is consistent with the start of olaparib therapy.

For drug exposure measured through quantitating olaparib by LC-MS/MS in a trough sample, trough concentrations between groups will be compared with non-parametric Wilcoxon signed rank test with significance set at P<0.05. If significant, we may explore ROC analyses.

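### The planned exposure–toxicity test splits patients into with and without toxicity, although maximum CTCAE grade is already recorded; analysing by grade is a cheap improvement

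*Combined protocol and SAP*

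**What the plan says.** Objective 1.2.10 is a listed secondary objective: "To explore exposure-response relationships between olaparib exposure and toxicity/efficacy". The exposure measure is a single value per patient; Section 11, note K, says "A mandatory trough plasma sample will be obtained only once at approximately 28 days after initiation of treatment".

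Two places describe the analysis. Section 10.1.6 says that troughs "will be compared between patients with/without response and patients with/without toxicity". Section 13.3.5 adds that "trough concentrations between groups will be compared with non-parametric Wilcoxon signed rank test with significance set at P<0.05", followed by "If significant, we may explore ROC analyses". No section relates trough to toxicity grade.

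Grade is nevertheless available. Section 13.3.3 states: "The maximum grade of toxicity for each category of interest will be recorded for each patient". It counts as toxicity any adverse event with at least a possible relation to treatment, and sets no minimum grade. Section 10.1.6 sets none either, and does not say whether the comparison is per category or pooled over categories.

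**The concern.** Toxicity is held on an ordered scale but tested on two levels. A patient with one grade 1 event and a patient with a grade 4 event fall in the same group, so the test says nothing about whether severity rises with exposure. That is a large part of what an exposure–toxicity question is for.

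The split can also leave one group small. Section 8.1 lists nausea in 58–77% of patients and fatigue in up to 67%. If a single grade 1 event in any category is enough, few patients will be without toxicity.

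At stake is the one planned test of this part of the objective. ROC work is foreseen only if that test is significant, so a weak test may also close off the follow-on analysis.

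**Working it through.** **The plan's own figure.** The documents give no power, effect size or sample size for objective 1.2.10. The only stated power, 90%, belongs to the primary test, and that is where n = 75 comes from. It reproduces. With hazard λ = ln 2/11 = 0.0630 per month and follow-up uniform on 18–42 months, the event probability is 1 − (e^(−18λ) − e^(−42λ))/(24λ) = 1 − (0.3217 − 0.0709)/1.512 = 0.834, or 62.6 events in 75 patients. Power is Φ(ln(11/8)·√62.6 − 1.2816) = Φ(1.24) = 0.89. So 75 is a sound planning number for the trial, but an upper bound for patients with a trough.

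**Inputs for the toxicity comparison**

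- From the documents: n = 75 (13.2); significance level 0.05 (13.3.5); nausea 58–77%, anemia 23–44% any grade and 7–21% grade 3–4 (8.1).
- Assumed: a two-sided test; a correlation of 0.30 between log trough and latent severity; pooled any-grade toxicity of 86% or 92%; the split of patients among individual grades.
- Test: rank-sum for the two-group comparison, because the groups are independent. The signed rank test named in 13.3.5 is a paired test; that is a separate matter and does not change this comparison.

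**Method.** Log trough X is standard normal and latent severity is Y = 0.30·X + √(1 − 0.30²)·ε. Y is cut into grades at the assumed percentages. Each simulated trial is tested twice: rank-sum of X between the two groups, and Spearman correlation of X with grade. With 3,000 trials per row, the standard error of a power figure is at most √(0.25/3000) = 0.9 points.

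| Toxicity definition (correlation 0.30, n = 75) | With/without | By grade | Gain (points) |
|---|---|---|---|
| Pooled, 92% any grade, cut at grade ≥1 | 28% | 68% | 40 |
| Pooled, 86% any grade, cut at grade ≥1 | 37% | 68% | 31 |
| Pooled, two grade splits, cut at grade ≥2 | 51–52% | 68–69% | 16–18 |
| Nausea 77% | 44% | 65% | 21 |
| Nausea 58% | 52% | 61% | 9 |
| Anemia 44% any, 21% grade 3–4 | 52% | 58% | 6 |
| Anemia 23% any, 7% grade 3–4 | 46% | 47% | 1 |

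Repeat runs with other assumed grade splits agree within a few points (for example 7 and 3 points for the two anemia rows).

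**Sensitivity to the assumed correlation** (n = 75, cut at grade ≥1; with/without against by grade)

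| Correlation | 90% any grade | 60% any grade |
|---|---|---|
| 0.1 | 7% vs 12% | 11% vs 12% |
| 0.2 | 16% vs 36% | 26% vs 34% |
| 0.3 | 31% vs 68% | 52% vs 65% |
| 0.4 | 50% vs 90% | 78% vs 88% |

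Over correlations of 0.1–0.6, 40–75 patients and cuts at grade 1, 2 or 3, the loss from splitting runs from 0 to 65 points. In this grid, which leaves out dose changes before sampling, splitting never raised power.

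**Dose changes before the sample.** Sections 6.3 and 7 provide for interruption and dose reduction after grade 3–4 events, and the only trough is at about day 28. Suppose 30% of patients with grade 3–4 toxicity have troughs lowered by 1 SD before sampling. The pooled gain then falls from 31–32 to 6–8 points (86% any grade) and from 40 to 11 (92%). At 50% of such patients, both tests are poor and the order reverses: 19% with/without against 12% by grade, and 17% against 13%.

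**The case against.** The strongest objection is that the size of the loss is not a property of this plan. The correlation, the pooled toxicity rate and the grade splits are all assumed, and the largest losses need the least favourable reading of an undefined term: any grade, pooled over categories. Section 13.3.3 works by category, and for anemia the gain is only 1–7 points. This stands. A reader might infer that the plan forfeits a fixed amount of power, or that it chose a badly placed cut. The documents support neither, because they state no cut.

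A reader might also extend the point to efficacy and treat response yes/no as a coarsened form of progression-free survival or time to next treatment. The documents do not support that. Best overall response (13.3.4) is an endpoint in its own right. The two event times start at enrollment and at the end of platinum therapy (1.2.1, 1.1.1), both before olaparib. Time from the PK sample to next treatment would be a new endpoint, and stopping for toxicity could shorten it, which would confuse an efficacy reading.

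The dose-change objection is real too: it shrinks the advantage of grading and can reverse it. But it distorts the with/without test as well, and Appendix L records the olaparib dose at sampling, so it can be examined.

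Finally, the objective is exploratory, has no power target and drives no dosing, stopping or primary decision. Nothing bars a later analysis by grade. That limits the severity but does not remove the case for planning the better analysis in advance.

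**Conclusion.** The point holds for toxicity only, at low severity. The plan's one exposure–toxicity test discards grade information that the trial already records, and it cannot address severity. That part follows from the text and needs no assumption.

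The size is conditional. At a correlation of 0.30 with 75 troughs and no dose change before sampling, the with/without test has about 27–53% power and rank correlation with grade about 48–70%. The gain is about 3 points or less for a toxicity seen in about a quarter of patients, 15–18 for a pooled grade ≥2 cut, and about 31–42 for pooled any-grade toxicity. At a correlation of 0.1 the gain is at most about 5 points with 75 patients. It also shrinks, and may vanish, if many patients with severe toxicity have had their dose lowered before the sample.

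**What to change.** In Sections 10.1.6 and 13.3.5, make the main exposure–toxicity analysis a Spearman correlation of log trough with maximum CTCAE grade of treatment-related toxicity, per category of interest and overall. A proportional-odds model would also serve. Keep the with/without toxicity comparison as a descriptive display, and state the grade that defines it.

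Add one sensitivity analysis based on the dose recorded in Appendix L: either a dose-normalised trough, or exclusion of patients whose dose changed before sampling. Exclusion selects partly on toxicity, so report it beside the main result and not in its place.

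Leave the response comparison as planned. An event-time analysis starting at the PK sample is an optional exploratory addition, not a correction.

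The cost is a few sentences and a little programming, with no new data, samples or patients. The downsides are the extra sensitivity analysis and, if proportional odds is chosen, one model assumption that Spearman does not need.

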11. STUDY CALENDAR

Baseline evaluations are to be conducted within 14 days prior to start of trial. Imaging CT scans and x-rays must be done ≤ 4 weeks prior to the start of therapy.

Procedure/Test	Pre- Study	Surveillance every 4 weeks	Day 1 of each cycle	Every 12 weeks	30 day follow- up*	Every 3 months
Informed consent	Х					
Demographics	Х					
Concurrent medications	Х	Х	Х		Х	
Medical history	Х					
Physical exam ^A	Х	Х	Х		Х	
Vital signs ^A	Х	Х	Х		Х	
Height and Weight ^A	Х	Х	Х		Х	
Performance status ^A	Х	Х	Х		Х	
CBC w/diff, platelets A	Х		Х		Х	
Serum chemistry A,B	Х		Х		Х	
CA125 ^A	Х	Х	Х		Х	
PTT/PT/INR ^C	Х					
EKG ^C	Х					
Tumor Measurements D	Х			Х		
Baseline signs & symptoms	Х					
Adverse event evaluation ^E	Х	Х	Х		Х	
Worry and Distress Measures ^F	Х	Х	Х		Х	
Quality of Life and Physical Function Measures ^G	Х			Х	Х	
Financial Toxicity Measures ^H	Х			Х	Х	
Urine or serum B-HCG for WOCBP ¹	X					
Tissue Collection ^J	Х				Х	
PK plasma sample ^K			ХК			

BRCA testing ^L	X			
Survival Follow-up ^M				Х

*Patients should be seen 30 days after completion of treatment to assess for resolution of toxicity

- A. These procedures do not need to be repeated in cycle 1 if done pre-study within 7 days prior to start of protocol therapy.
- B. Albumin, alkaline phosphatase, total bilirubin, direct bilirubin, bicarbonate, BUN, calcium, chloride, creatinine, glucose, potassium, total protein, SGOT [AST], SGPT [ALT], sodium, magnesium, phosphorus
- C. Required pre-study, then as clinically indicated
- D. Prior to olaparib initiation, imaging will only be done for doubling of nadir CA125 or per physician discretion for patient symptoms. Following initiation of olaparib, CT scans will be obtained every 12 weeks as part of surveillance. CT scans can be obtained for rising CA125 or physician preference for patient symptoms before scheduled routine surveillance.
- E. Adverse event evaluation will include both the CTCAE and the PRO-CTCAE (See Appendix D).
- F. Worry and distress measured via Assessment of Survivor Concerns (ASC) (See Appendix E) worry subscale and Impact of Event Scale (IES-R) (See Appendix F).
- G. Health-related quality of life will be measured via The Functional Assessment of Cancer Therapy + Ovarian-specific scale (FACT-O) (See Appendix G) and physical function assessed through the PROMIS Physical Function-20a assesses self-reported performance of physical activities (See Appendix H).
- H. Financial toxicity will be measured through a) monetary measure using the Modified Collection of Indirect and Nonmedical Direct Costs (COIN) (See Appendix I), b) objective measure of financial burden assessed using Barrera et al.'s Economic Hardship questionnaire (See Appendix J), and c) subjective measure of financial distress will be gauged using the Comprehensive Score for Financial Toxicity (COST Measure) (See Appendix K).
- I. Pregnancy test for women of childbearing potential (WOCBP) must be done within 24 hours prior to initiation of olaparib.
- J. Tissue collection is not mandatory. If permission granted, tissue prior to initiation on olaparib will be obtained from archival stores. If patient undergoes biopsy at the time of progression as part of standard of care, tissue will be collected after routine processing.
- K. A mandatory trough plasma sample will be obtained only once at approximately 28 days after initiation of treatment (See **Appendix L**).
- L. BRCA testing required (Results not needed for registration
- M. Chart review or office visit every 3 months for 18 months from time of enrollment

12. MEASUREMENT OF EFFECT

Although not all patients will have measurable disease, patients with partial response to the previous platinum-based therapy are eligible for this study, and they will be carefully monitored for tumor response and symptom relief in addition to safety and tolerability. Patients will be assessed by standard criteria. For this study, patients will undergo a clinical assessment every 4 weeks while receiving olaparib. Tumor response will be evaluated at 12 week intervals.

12.1. Antitumor Effect – Solid Tumors

Response and progression will be evaluated in this study using the new international criteria proposed by the revised Response Evaluation Criteria in Solid Tumors (RECIST) guideline (version 1.1) [*Eur J Ca* 45:228-247, 2009]. Changes in the largest diameter (unidimensional measurement) of the tumor lesions and the shortest diameter in the case of malignant lymph

nodes are used in the RECIST criteria.

12.1.1. Definitions

Evaluable for toxicity. All patients will be evaluable for toxicity from the time of their first treatment with olaparib.

Evaluable for objective response by RECIST. Patients who have received at least 1 cycle of therapy and have had their disease re-evaluated with a 3-month post treatment CT will be considered evaluable for response. These patients will have their response classified according to the definitions stated below. (Note: Patients who exhibit objective disease progression prior to the end of cycle 1 will also be considered evaluable.)

Evaluable for objective response by CA-125. Patients who have received at least 1 cycle of therapy, have a CA-125 before treatment below the upper limit of the normal (for values above this limit, any increase in a second sample has to be <15% increase) and have had their disease re-evaluated with monthly CA125, will be considered evaluable for response. These patients will have their response classified according to the definitions stated below. (Note: Patients who exhibit objective disease progression prior to the end of cycle 1 will also be considered evaluable.)

Evaluable Non-Target Disease Response. Patients who have lesions present at baseline that are evaluable but do not meet the definitions of measurable disease, have received at least one cycle of therapy, and have had their disease re-evaluated, will be considered evaluable for non-target disease. The response assessment is based on the presence, absence, or unequivocal progression of the lesions.

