Endoscopy, Laparoscopy: The utilization of these techniques for objective tumor evaluation is not advised. However, such techniques may be useful to confirm complete pathological response when biopsies are obtained or to determine relapse in trials where recurrence following complete response (CR) or surgical resection is an endpoint.

Tumor markers: If markers are initially above the upper normal limit, they must normalize for a patient to be considered in complete clinical response. Specific guidelines for both CA-125 response in recurrent ovarian cancer have been published [*JNCI* 96:487-488, 2004; *J Clin Oncol* 17, 3461-3467, 1999; *J Clin Oncol* 26:1148-1159, 2008]. In addition, the Gynecologic Cancer Intergroup has developed CA-125 progression criteria

which are to be integrated with objective tumor assessment for use in first-line trials in ovarian cancer [*JNCI* 92:1534-1535, 2000].

Cytology, Histology: These techniques can be used to differentiate between partial responses (PR) and complete responses (CR) in rare cases (*e.g.*, residual lesions in tumor types, such as germ cell tumors, where known residual benign tumors can remain).

The cytological confirmation of the neoplastic origin of any effusion that appears or worsens during treatment when the measurable tumor has met criteria for response or stable disease is mandatory to differentiate between response or stable disease (an effusion may be a side effect of the treatment) and progressive disease.

FDG-PET: While FDG-PET response assessments need additional study, it is sometimes reasonable to incorporate the use of FDG-PET scanning to complement CT scanning in assessment of progression (particularly possible 'new' disease). New lesions on the basis of FDG-PET imaging can be identified according to the following algorithm:

- a. Negative FDG-PET at baseline, with a positive FDG-PET at follow-up is a sign of PD based on a new lesion.

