12.1.4.2 Evaluation of Non-Target Lesions

Complete Response (CR): Disappearance of all non-target lesions and normalization of tumor marker level. All lymph nodes must be non-pathological in size (<10 mm [<1 cm] short axis).

Note: If tumor markers are initially above the upper normal limit, they must normalize for a patient to be considered in complete clinical response.

Non-CR/Non-PD: Persistence of one or more non-target lesion(s) and/or maintenance of tumor marker level above the normal limits.

Progressive Disease (PD): Appearance of one or more new lesions and/or *unequivocal progression* of existing non-target lesions. *Unequivocal progression* should not normally trump target lesion status. It must be representative of overall disease status change, not a single lesion increase.

Although a clear progression of "non-target" lesions only is exceptional, the opinion of the treating physician should prevail in such circumstances, and the progression status should be confirmed at a later time by the review panel (or Principal Investigator).

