12.1.4.3 Evaluation Based on CA125

Complete Response (CR): Normalization of CA-125 levels. The response must be confirmed and maintained for at least 28 days. No new or progressive disease on imaging.

Partial Response (PR): At least a 50% reduction in CA-125 levels from a pretreatment sample but not reaching normalization. The response must be confirmed and maintained for at least 28 days. No new or progressive disease on imaging.

Progressive Disease (PD):

- Patients with elevated CA-125 pretreatment and normalization of CA-125 must show evidence of CA-125 greater than, or equal to, 2 times the upper limit of the reference range on 2 occasions at least 1 week apart or
- Patients with elevated CA-125 before treatment, which never normalizes, must show evidence of CA-125 greater than, or equal to, 2 times the nadir value on 2 occasions at least 1 week apart or

- Patients with CA-125 in the reference range before treatment must show evidence of CA-125 greater than, or equal to, 2 times the upper limit of the reference range on 2 occasions at least 1 week apart
- Response determined via measurable disease (measurement of target and nontarget lesions) takes precedence over CA-125 criteria

Stable Disease (SD): CA-125 fluctuations not fitting above criteria

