13.3.4 Analysis of Efficacy Endpoints

Allowing 18 months of follow-up following the last patient accrual, time to next treatment will be estimated by the Kaplan-Meier method. Median time to next treatment will be estimated with 90% confidence intervals. The maximum likelihood estimate of the hazard rate (hazard of next treatment) will be calculated and used to conduct a one-tailed

exponential test at level alpha = .10. This will test the hypothesis that time to next treatment is increased over that expected for olaparib without delay (this assumes the data follow an exponential distribution, otherwise, an alternate parametric test or a one sample log rank test will be used). Toxicities will be summarized by grade, frequency and attribution to olaparib. Median progression-free survival (PFS) and overall survival (OS) will be estimated using the Kaplan Meir method. The Kaplan-Meier method with a log rank test will be applied to test differential response by mutation status. We will estimate the response rate utilizing RECIST and/or GCIG criteria. For those patients with measurable disease and elevated CA125, both RECIST and GCIG criteria will be utilized. For those without measurable disease, GCIG criteria alone will be used to record response. Overall response will be defined as the number of patients with best overall response of CR and PR. The effect of treatment will be reported with its supporting 90% confidence interval.

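### CA-125 evaluability in Section 12.1.1 does not fit the CA-125 response criteria, RECIST evaluability hangs on a 3-month CT, and no rule chooses between two candidate denominators for the response rate

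*Combined protocol and SAP*

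**What the plan says.** **CA-125 route.** Section 12.1.1 treats a patient as evaluable if, after at least one cycle and with monthly CA-125 follow-up, she is among those who "have a CA-125 before treatment below the upper limit of the normal (for values above this limit, any increase in a second sample" must be below 15%). Neither sample is dated. Section 12.1.4.3 then defines CR as normalization, confirmed and held for 28 days, and PR as "At least a 50% reduction in CA-125 levels from a pretreatment sample but not reaching normalization". For a normal start it gives a progression rule: "Patients with CA-125 in the reference range before treatment must show evidence of CA-125 greater than" or equal to twice the upper limit on two occasions. Stable disease is whatever fits none of these.

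**RECIST route.** Section 12.1.1 says that patients with at least one cycle who "have had their disease re-evaluated with a 3-month post treatment CT will be considered evaluable for response". A note adds those with objective progression before cycle 1 ends. The non-target route has no such CT condition: patients who "have received at least one cycle of therapy, and have had their disease re-evaluated, will be considered evaluable for non-target disease".

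**Analysis.** Section 13.3.4 says "For those patients with measurable disease and elevated CA125, both RECIST and GCIG criteria will be utilized", and uses GCIG alone where disease is not measurable. It defines overall response as a count of patients whose best response is CR or PR. Section 13.3.1 assigns all eligible patients who begin treatment to the efficacy endpoints.

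**Endpoint.** Section 1.2.4.1 names RECIST v1.1 only. The synopsis and Section 14.1 say RECIST or CA-125.

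**The concern.** A patient should count as evaluable for response only if the criteria allow her to respond. The main clause of the CA-125 definition selects patients for whom PR is impossible and CR is either automatic or empty. Elsewhere the protocol uses normalization in the opposite sense. Section 12.1.3 says "If markers are initially above the upper normal limit, they must normalize for a patient to be considered in complete clinical response", and Section 12.1.4.2 repeats the rule: "If tumor markers are initially above the upper normal limit, they must normalize for a patient to be considered in complete clinical response".

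The RECIST definition conditions on surviving and staying in follow-up until a scan. A treated patient lost before that scan leaves the set, and if she was not a responder the rate rises.

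The response rate is a secondary endpoint, stratified by BRCA status. Response also forms the groups for the trough-concentration comparison in Section 10.1.6. Two analysts following the text could derive different numerators and denominators from the same data.

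**Working it through.** **1. The plan's own figure.** Section 13.2 (Sample Size) cites Study 19: 61 patients evaluable for response, 16 responders by RECIST and 1 by CA-125. 16/61 = 26.2% and 1/61 = 1.6%, so both reproduce. The plan sets no target or precision for its own response rate.

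**2. A normal starter.** Write U for the ULN.
- Section 6.1 starts olaparib at twice the nadir, with no minimum value. Section 5 takes baseline as the reference, also with no minimum.
- Nadir 0.4U: the trigger is 2 × 0.4U = 0.8U, still normal.
- PR needs a value of at most 0.5 × 0.8U = 0.4U. That is within the normal range, so the requirement to stop short of normal fails. For any start x < U, 0.5x < 0.5U, so PR is never possible.
- CR: the value was normal before the first dose, so normalization has no content.
- PD needs at least 2U twice. SD is the residual class.

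Only SD and PD can sensibly be scored. If she has no measurable disease, Section 13.3.4 sends her to GCIG alone.

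**3. The 15% clause, which applies to values above U.**
- Read as nadir N against trigger sample, both above U: the rise is at least (2N − N)/N = 100%, which exceeds 15%, so no such patient qualifies.
- Read as two samples taken after the trigger is met: the calendar schedules CA-125 on Day 1 of each cycle, so a second value will often exist. Footnote A waives the cycle 1 draw if one was done within 7 days before therapy. The text does not say which reading is meant.

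**4. The RECIST gap.** Cycle 1 ends at day 28. Scans are every 12 weeks, 12 × 7 = 84 days. The exception leaves 84 − 28 = 56 days uncovered. On the literal wording, a patient who dies, stops, or progresses on an unscheduled CT in that window and never has the 3-month CT is not RECIST-evaluable.

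**5. Size of (4), with assumed shares.** Let p be the rate in all treated patients and k the share dropped, all non-responders. The evaluable-set rate is p/(1 − k). Take p = 26.2% only as a convenient starting value.
- k = 0.10: 0.262/0.90 = 29.1%
- k = 0.20: 0.262/0.80 = 32.8%

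Because 16/61 is itself an evaluable-set rate, the reverse reading is p(1 − k): 23.6% or 21.0% in all treated patients.

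**6. CA-125 effect.** No figure is given. The documents do not state what share of patients start below the ULN, and the 26.2% is a RECIST rate, against 1.6% by CA-125.

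**The case against.** The plan is less bare than it may look, and several stronger readings fail.

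- A reader might infer that a normal starter can be classified only as PD. Section 12.1.4.3 also defines SD, so she can be scored as a non-responder. What stays unresolved is CR.
- A reader might infer that nothing says how the routes combine. Section 12.1.4.3 gives measurable-disease response precedence over CA-125, and Section 13.3.4 says which criteria apply with and without measurable disease.
- A reader might infer that there is no denominator at all. Section 13.3.1 assigns an efficacy set to efficacy endpoints, and response is analysed under that heading. If that set governs, the inflation from the 3-month CT does not arise. The defect is that Section 12.1.1 defines a competing evaluable set and no sentence chooses.
- A reader might infer that the 15% clause excludes every elevated starter. It does so only on the nadir-versus-trigger reading, and only when the nadir was already above the ULN.
- The adopted GCIG criteria may date the two samples. They are cited but not reproduced, so this cannot be settled from the documents.
- The historical 16/61 is an evaluable-set rate, so an evaluable-set rate is arguably the comparable one. That is a fair reason to report it, but not to leave the main denominator open.

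These points narrow the finding. They do not reconcile Sections 12.1.1 and 12.1.4.3, and they do not supply the missing rule.

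**Conclusion.** The point holds in three parts. First, CA-125 evaluability admits patients who cannot have a PR and for whom CR is undefined. This follows from the wording and the trigger arithmetic; how many patients it touches is unknown. Second, RECIST evaluability depends on a 3-month CT with a narrow exception, and that set competes with the Section 13.3.1 efficacy set without a rule. The upward shift, 26.2% to 29.1% or 32.8%, rests on assumed shares of 10% and 20% and on every dropped patient being a non-responder. Some may remain evaluable by the CA-125 or non-target route, which do not require that CT. Third, Section 1.2.4.1 disagrees with the synopsis and Section 14.1.

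A reader might infer that the trial's main conclusion is at risk. It is not: the primary endpoint is time to next therapy, and neither its test nor the 75 patients depend on response. This is a secondary-endpoint definition that should be corrected before response is analysed.

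**What to change.** - **12.1.1:** require a pre-olaparib CA-125 above the ULN for CA-125 response evaluability. State which two samples the 15% clause compares and at what interval, checked against the adopted GCIG criteria and reconciled with the doubling trigger.
- **12.1.4.3:** say that CA-125 CR and PR apply only when the pre-treatment value is elevated.
- **13.3.4:** name the denominator as efficacy-set patients who at olaparib start have measurable disease (RECIST) or elevated CA-125 (GCIG). Keep the existing precedence rule and the existing rule on which criteria apply.
- Do not make inclusion depend on the 3-month CT. Count progression on any CT as PD, and treated patients with no post-baseline assessment as non-responders.
- Report the Section 12.1.1 evaluable-set rate as a sensitivity analysis, which keeps comparability with 16/61. Report the number of patients assessable by neither route.
- **1.2.4.1:** align with the synopsis and Section 14.1.

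The cost is wording; CA-125 and CT are already collected, including a CT at the trigger. The reported rate may be slightly lower and fewer patients may be CA-125-evaluable. Counting unassessed patients as non-responders is a conservative convention that the documents do not themselves require, so it should be stated as a choice.
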